“Nerve block analgesia” is not necessarily synonymous with “nerve block numbness.” Analgesia is “pain relief,” and pain relief without numbness is thought to promote early physical therapy. Nerve block numbness (even though the numbness is indeed providing pain relief) is expected to delay physical therapy due to lack of muscle strength during numbness. One of the goals of the study’s exploratory aims is to determine if the MMPNA 4-drug combination provides both improved pain relief and improved physical therapy in the days after surgery (when compared with plain bupivacaine).

Anesthesia planning for invasive orthopedic surgery after battlefield-sustained polytrauma above and below the abdomen typically requires general endotracheal anesthesia (GETA) for surgical stabilization of all traumatic injuries. However, based on recent anesthetic innovations, GETA is no longer required for elective TKA/THA, and therefore GETA is not specifically required for one-sided lower-extremity polytrauma. For TKA/THA, the exclusive use of RegA (without GETA) is not only feasible and sufficient, but also comparatively effective via reductions in morbidity and mortality (based on population data).⁽²⁾ GETA has temporary adverse effects on immediate postoperative cognitive function after surgery, and the cognitive risks after multiple episodes of GETA is unknown but is unlikely to be beneficial long term. Eliminating GETA as a confounder of immediate physical therapy / occupational therapy (PT/OT) outcome evaluation now allows for proper evaluation of anesthesiologist physician-directed pain relief, and this study of veteran-specific care has the potential to immediately translate to the care of injured military personnel.

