For patient-reported outcome of function, we will use the data generated by Western Ontario and McMaster Universities Osteoarthritis Index Physical Function Subscale (WOMAC-PF). The entire WOMAC instrument will be administered. This instrument was developed based on patient input and is the instrument of choice to assess outcome post-TKA and THA (20). The WOMAC-PF consists of 17 items related to physical function. Each item is scored on a 5-point Likert-type Scale with descriptors from 0-4 (none, mild, moderate, severe, and extreme difficulty). Scores of each item are summed for a maximum total score on the WOMAC-PF of 68. Higher scores indicate worse functional limitations. Reliability and validity of this instrument have been established (25-27). This will be given before surgery and at Follow-Up Visit 2 after surgery. Licensing rights to this questionnaire have been purchased by the study team for use in this research study.

Falls Questionnaire:

Throughout the study, the patients will be asked about their falls history. The information collected will include but is not limited to, how many falls the patient experienced in the past year (done at baseline), how many falls since the last assessment (in-hospital visits and Follow-Up Visit 2), questions regarding loss of balance, whether or not the patient is afraid of falling, and was medical treatment sought after any falls.

Clinical Assessments

None of the clinical assessments listed below are being done due to safety concerns, as such, if the physical therapist or treating physician feels that due to the patients' medical condition (such as a knee immobilizer), that some or all of the physical therapy tests cannot be completed at the specified protocol time points; the physical therapy testing will be considered optional for these patients and will be done at the discretion of the treating physician and physical therapist. If physical therapy testing is not completed due to the patient preparing for discharge and/or the patient has been discharged, this will not be considered a protocol deviation.

Gait Speed: Self-selected gait speed is measured in meters/second while subjects walk a 4 meter path located in the middle of a longer path of 9 meters to avoid acceleration or deceleration. Subjects are asked to walk at their regular pace, and time is measured with a stop watch. This test takes around 2 minutes.

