5.0 Statistical Analysis

5.1 Analysis Plan

Data will first be assessed for outliers (+/- 2 SD from the mean) and normality. Outliers will be corrected, if possible, or dropped from the analyses. Distribution, measures of central tendency, variability, and normality will be examined. Data transformations or non-parametric techniques will be applied as needed. We will delete observations with missing values. Spearman correlation coefficients will be computed to examine associations between nerve block drug treatments, replacement surgery

type (hip versus knee), and the outcome measures (SF-MPQ, SF-8, SF- 36, WOMAC, FIM, repeated chair stand test, Opioid Symptom Distress Scale, Defense and Veterans Pain Rating Scale and its Supplemental Questions) from all time points (1 day, 2 day, 3 day, 4 day, Follow-Up Visit 1, Follow-Up Visit 2). Associations between the outcomes across time points will also be examined with Pearson (SF-MPQ, SF-8, SF-36, WOMAC, repeated chair stand test, Opioid Symptom Distress Scale) and Spearman (FIM, Defense and Veterans Pain Rating Scale and its Supplemental Questions) correlation coefficients. We will test all hypotheses and aims by conducting longitudinal multi-level modeling. The level-one unit will be the repeated measures across time, the level-two unit will be the individual patient, and the level-three unit will be nerve block type and surgical site (knee versus hip) groupings (with additional analyses involving age and diabetes status, reflecting the randomization strata). This mixed model procedure will allow the assessment of outcome and exposure variables relationships while adjusting for covariates, and separate assessments of fixed and random effects (i.e., group and individual-level data) using highly correlated repeated measures data. Covariates included in modeling will be age, diabetes status, gender, weight, smoking status, initial health status (e.g., baseline SF-8 / SF-36 and WOMAC), and concurrent general health status (e.g., daily SF-8, subsequent SF-36, and WOMAC).

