The **primary hypothesis** of an improvement in pain (measured by the SF-MPQ- version 2) 24 hr after surgery during in-hospital recovery comparing plain local anesthetics versus ISOC MMPNA will be tested using a mixed model. This procedure will test for nerve block drug treatment and surgical site (hip versus knee) effects, as well as an interaction between them. Differences in pain levels will also be examined across the study's day-of surgery, 1, 2, 3, and 4 day, and Follow-Up Visit 1 and Follow-Up Visit 2 time points. The secondary aims of short- and long-term physical therapy and rehabilitation-related benefits will also be examined for nerve block drug treatment and surgical site by a mixed model. The tertiary aim to determine differences in opioid-related side effects will use a mixed model. As with other analyses, there will be an examination for nerve block drug treatment and surgical site effects, as well as an interaction between them, along with analyses of the other randomization strata (age, diabetes) as described above.

The **exploratory aims** of physical therapy progress, return-to-home benefits, etc. will be examined using a mixed model. This procedure will test for nerve block type and surgical site effects, as well as an interaction between them. Number of days from the joint replacement procedure to the patient's home discharge will be assessed. Pain responses, as measured by the SF-MPQ – version 2, and use of postoperative opioids with additional measurement by the Opioid-Related Symptom Distress Scale will also be assessed. General health status will be evaluated with the SF-8 and SF-36. Measures of pain, analgesic side-effects, and general health status will be covariates included in the modeling of the effect of MMPNA on return-to-home.

Only after all data are analyzed and results are checked and verified by the biostatisticians will the study be unblinded.

5.2 Adverse Events. For adverse events, we will calculate cumulative probability using survival analysis techniques such as the product-limit estimator. Unlike proportions, product-limit estimators can be applied at various times following randomization, and can take into account when adverse events occur. The six-week incidence (and 95% CI) of individual adverse events by organ system and relatedness to the study will be calculated for each group. We will estimate the incidence of adverse

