If potential subjects decide not to participate in this research study, they will undergo TKA/THA surgery and be offered the routine choices of anesthetic currently offered to our patients undergoing the same procedure. The same spinal and MMPNA nerve block techniques are used as our ISOC. For TKA patients that have spine-specific contraindications, there are other ISOC nerve block techniques used (e.g., the psoas compartment lumbar plexus and sciatic nerve blocks for surgical anesthesia and postoperative analgesia, or “lum-sci” for short). It is conceivable that TKA patients (opting not to participate in the study) without spine abnormalities may be offered a lum-sci as part of ISOC. However, this lum-sci block leads to a more profound postoperative numbness that can preclude the study-specific physical therapy protocol from reliably commencing on the morning of postoperative day 1. THA routinely involves spinal anesthesia (and the described ISOC MMPNA blocks) if there are no contraindications (to the spinal such as previous spine fusion or spinal cord stimulator), depending on the clinical situation and other health status factors. Local anesthetics used for our routine nerve blocks (i.e., bupivacaine, for patients not participating in the study) are the same as those used in the study (both ISOC MMPNA and Active Control). In our ISOC, nerve block patients receive all 4 drugs in the nerve blocks (the local anesthetic and the 3 other CBD drugs), even though we do not know (by formal study) if the 4-drug nerve block gives longer-acting pain relief, or longer-acting unwanted numbness, than does the nerve block with use of only the local anesthetic. Patients may have a history of allergy to Novocain®; our nerve blocks do not use Novocain itself, and so the risk of allergy from other local anesthetics that we use for patients is exceedingly rare. Many medical centers performing TKA/THA surgery do not routinely offer patients a choice in anesthesia technique, and most medical centers do not offer nerve blocks of any kind for TKA/THA surgery. However, MMPNA nerve blocks are the ISOC at VAPHS, and the anesthesia doctors who perform these nerve blocks here are very well-experienced.

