APPENDIX 1: Study Calendar

	Screening Visit ^a	Baseline Visit	Day of surgery		Post-Op Day 1	Post-Op Day 2	Post-Op Day 3	Post-Op Day 4	Post-Op Day 5	Follow-Up Visit 1 ^d	Follow-Up Visit 2 ^{c, e}
			Pre-Procedure	Post-Procedure							
Clinical Assessments											
Informed Consent	X										
Determine Eligibility	X										
Demographics	X										
Orthopedic & IMPACT evaluation		X									
Crude Sensation in L2-L4 & L4-S3		X			X	X	X	X	X		X
Straight Leg Raise & Range of Motion		X			X	X	X	X	X		X
Functional Independent Measure (FIM)		X			X	X	X	X	X		X
Standing Balance Test		X			X	X	X	X	X		X
Single Leg Balance Test ^g		X									X
Gait Speed		X			X	X	X	X	X		X
Repeated Chair Stand Test		X				X	X	X	X		X
Stair Climbing Time		X									X
Physical Therapy/ Therapeutic Exercises					X	X	X	X	X		
Comorbidity (CIRS)		X									
Interim Changes											X
Discharge Disposition											X
Opioid Consumption					X ^g						
Anesthesia/Study Drugs			X								
Adverse Events		X	X	X	X	X					
Concomitant Medications		X	X	X	X	X					

	Screening Visit	Baseline Visit	Day of surgery		Post-Op Day 1	Post-Op Day 2	Post-Op Day 3	Post-Op Day 4	Post-Op Day 5	Follow-Up Visit 1	Follow-Up Visit 2 ^{c, e}
			Pre-Procedure	Post-procedure							
Questionnaires											
SFMPQ-2 ^b		X	X	X	X	X	X	X	X		X
DVPRS		X	X	X						X	X
DVPRS- in hospital ^b					X	X	X	X	X		
ORSDS ^b		X			X	X	X	X	X		
QOR-15 ^b		X			X	X	X	X	X		X
WOMAC		X									X
SF-8 ^b			X		X	X	X	X	X	X	
SF-36		X									X
Falls Questionnaire		X			X	X	X	X	X		X

a. The screening visit and baseline visit can be completed on the same day.

b. On post-op hospital days and post-op week 6 follow-up visits, these questionnaires will be completed before the subject has their first physical therapy session for the day.

c. If a patient decides to withdraw from the study after having their surgery, or is withdrawn by the study team during or after their surgery, they will be asked to complete Follow-Up Visit 2.

d. Follow-up visit 1 will occur with the patient's already scheduled standard of care follow-up orthopedic visits. Follow-Up Visit 1 may be performed as a phone call if necessary.

e. Follow up visit 2 will be scheduled to coincide with the patient's standard of care follow-up orthopedic visits.

f. Patient must pass the standing balance test first, before the single leg balance test can be attempted.

g. Opioid consumption will stop being collected at the time of the patient's discharge.

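### The covariate list that governs the primary 24-hour pain model includes health status measured after the block, so the adjusted coefficient is not the total effect of the block

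*Combined protocol and SAP*

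**What the plan says.** Section 5.1 states its scope first: "We will test all hypotheses and aims by conducting longitudinal multi-level modeling". It then gives a single covariate list: age, diabetes, gender, weight, smoking, initial health status and, as a separate item, "concurrent general health status (e.g., daily SF-8, subsequent SF-36, and WOMAC". The primary hypothesis is an improvement in SF-MPQ-2 pain "24 hr after surgery during in-hospital recovery comparing plain local anesthetics versus ISOC MMPNA will be tested using a mixed model". That paragraph names treatment, surgical site and their interaction. It gives no covariate list of its own and does not set the general list aside.

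The same section counts the health-status instruments among the "outcome measures (SF-MPQ, SF-8, SF- 36, WOMAC, FIM" and others.

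The blocks are placed before the spinal anesthetic (section 4.1). Appendix 1 schedules SF-8 pre-procedure on the day of surgery, on Post-Op Days 1 to 5 and at Follow-Up Visit 1. Footnote b is attached to both SF-MPQ-2 and SF-8 and says that on post-op hospital days "these questionnaires will be completed before the subject has their first physical therapy session for the day". After surgery, SF-36 and WOMAC appear only at Follow-Up Visit 2. Section 4.3 confirms this for WOMAC: "This will be given before surgery and at Follow-Up Visit 2 after surgery".

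For the exploratory return-to-home analysis, section 5.1 adjusts the effect of MMPNA for pain, analgesic side effects and general health status.

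**The concern.** Randomization makes the arms comparable at the time of the block. A variable measured later can itself be changed by the block, and conditioning on it gives up that comparability. The Post-Op Day 1 SF-8 is such a variable: it is completed after the block and in the same pre-therapy window as the Day 1 SF-MPQ-2.

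The consequence depends on how the block affects SF-8.

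- **Only through pain relief.** The test keeps its type I error, but the estimate shrinks toward zero and power may be lost. A positive result would be conservative.
- **Also by another route.** Type I error is no longer controlled. Worsened SF-8 pushes the pain estimate toward benefit, and improved SF-8 pushes it toward harm.

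The plan cannot say which case applies. Section 7.3 says it is not known "if the 4-drug nerve block gives longer-acting pain relief, or longer-acting unwanted numbness". The comparison at stake is the trial's one specific aim.

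**Working it through.** **Does the list reach the primary model?** The scope sentence covers all hypotheses, the list follows it as a flat statement, and the primary paragraph offers no alternative. As written, it does.

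**Which listed variable is operative at 24 hours?** Taking Post-Op Day 1 as the 24-hour assessment (read from Appendix 1, not stated outright), only SF-8 is collected then. Postoperative SF-36 and WOMAC come after the endpoint. Entered as patient-level covariates, they would be post-block as well.

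**Size.** The plan has no figure to reproduce here. Its only power statement (section 5.6) concerns block duration, and that section says no preliminary SF-MPQ data exist. What follows is an illustration with assumed inputs, for one time point.

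Score pain and SF-8 so that higher is worse, in within-arm SD units. Let d be the reduction in pain due to the block, g the improvement in SF-8, and r the within-arm correlation. In a linear model of pain on treatment and SF-8:

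- adjusted effect = d − r·g, so share recovered = 1 − r·(g/d)
- standard error = √[(1 − r²)(1 + q·g²)·N/(n₁n₂)], with q = n₁n₂/N²
- power from the noncentral t with N − 3 df, two-sided 5%

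For 20 vs 80, q = 1,600/10,000 = 0.16 and n₁n₂/N = 16. An unadjusted test with 80% power needs d = 0.707, a hypothetical value.

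Example with r = 0.5 and g = d: adjusted effect 0.707 − 0.354 = 0.354; standard error √(0.75 × 1.08/16) = 0.225; noncentrality about 1.57; power 34.3%.

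Each cell gives share of the true effect recovered / power at 20 vs 80:

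| Effect on SF-8 | r = 0.3 | r = 0.5 | r = 0.7 |
|---|---|---|---|
| None (g = 0) | 100% / 83.6% | 100% / 89.9% | 100% / 97.5% |
| Only through pain (g = r·d) | 91% / 75.9% | 75% / 67.1% | 51% / 50.1% |
| As much as pain (g = d) | 70% / 50.7% | 50% / 34.3% | 30% / 20.5% |
| Worsens half as much (g = −d/2) | 115% / 91.7% | 125% / 97.9% | 135% / 99.9% |

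**Type I error.** Set d = 0. If SF-8 moves only through pain, then g = 0 and the size is 5.0%. If the block shifts SF-8 by 0.3 SD through another route, the adjusted effect at r = 0.5 is 0.15 SD in absolute value, the standard error is √(0.75 × 1.0144/16) = 0.218, and the test rejects 10.5% of the time. For r = 0.3 / 0.5 / 0.7:

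- 20 vs 80: 6.6% / 10.5% / 21.2%
- 40 vs 160 (procedures combined): 8.2% / 16.2% / 37.6%

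Simulation at 20 vs 80 and r = 0.5 (20,000 trials) gave 4.96% when SF-8 moves only through pain and 10.9% with the 0.3 SD shift.

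**The case against.** **The list may be a menu.** The primary paragraph names no covariates, while the return-to-home sentence names concurrent measures explicitly, which would be partly redundant if the general list entered every model. The list also cannot apply literally everywhere, since SF-8, SF-36 and WOMAC are themselves outcomes. This reading is possible but less natural. It would leave the primary covariate set unspecified, and nothing in the plan limits that set to pre-block variables.

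**The non-pain route may be weak at Day 1.** Section 2.1 says numbness "is expected to delay physical therapy due to lack of muscle strength during numbness", but the Day 1 SF-8 precedes the first therapy session, so delayed therapy cannot explain it. This point stands. Each block has the same bupivacaine concentration in both arms (section 3.6), the adjuvants are called motor sparing (section 2.2), and numbness is put at a theoretical 12-16 hours (section 5.2). The plan therefore expects little difference in numbness at 24 hours. With a 0.1 SD shift, size at 20 vs 80 and r = 0.5 is only 5.6%. Direct effects of numbness or side effects on SF-8 remain open, because section 7.3 calls the matter unknown.

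**The arithmetic is for a simpler model.** The plan specifies a longitudinal multilevel model. With a common SF-8 slope and a patient random intercept, simulation under assumed values with cross-sectional r = 0.5 gave slopes from 0.34 to 0.66. For g = d the share recovered would then run from 66% to 34% instead of 50%. The direction is unchanged, but the percentages do not carry over exactly.

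**The table is not a bound.** At r = 0.7, g = −d gives 170% and g = 2d gives −40%. This is correct; the table covers only the values chosen.

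**Return-to-home.** The plan does not say when those covariates are measured, and pain and ORSDS are also collected at baseline. Post-block timing is likely but inferred.

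**Conclusion.** The concern holds and must be fixed. Followed as written, the primary model adjusts for a post-block variable and does not estimate the total effect of the block on 24-hour pain. Only if the block leaves the Day 1 SF-8 unchanged does the coefficient equal the total effect (and power may then rise). A plan that lists SF-8 as an outcome cannot assume that.

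Over the assumed values shown, where SF-8 is affected, the share of the effect recovered runs from 30% to 135%. Type I error runs from 5.0% to 21.2% at 20 vs 80 for a non-pain shift of up to 0.3 SD. These figures illustrate and do not predict. They rest on assumed correlations and SF-8 effects, a single-time-point linear model, and Post-Op Day 1 being the 24-hour assessment. In the pain-only case a positive finding would be conservative.

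The return-to-home model probably has the same problem: section 2.2 anticipates that rebound pain will hold back therapy objectives, so adjusting for pain may remove part of the effect being studied. That model is exploratory and does not set the severity.

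**What to change.** In section 5.1, delete concurrent general health status from the covariates of the primary model and of every model reported as a treatment effect. State that these models use only variables measured before the block: procedure, age, diabetes, gender, weight, smoking, baseline SF-36 and baseline WOMAC. Baseline Visit SF-MPQ-2 may be added for precision.

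Use the pre-procedure SF-8 only if it is confirmed to be completed before the block. Appendix 1 has no SF-8 at the Baseline Visit and puts the pre-procedure form in the same column as study drug administration, and the documents do not give their order.

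Report any model containing concurrent health status separately, labelled exploratory or mediation. Label the return-to-home model with post-treatment covariates the same way, and give a version without them as the treatment-effect estimate.

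The cost is SAP wording, plus one procedural confirmation if the pre-procedure SF-8 is to be used. The named baseline covariates are already collected. Make the change before unblinding, so that the choice of covariates cannot be questioned afterwards.

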ISOC MMPNA Block Group (n=80 TKA and 80 THA patients) will receive the ISOC 4-drug MMPNA nerve blocks at the L2-L4 and L4-S3 nerves/plexi. These blocks will be placed before the administration of spinal anesthesia, per our ISOC.

Active Control Block Group (n=20 TKA and 20 THA patients) will receive “active control” nerve blocks comprised of plain bupivacaine. As with the ISOC MMPNA Block Group, these blocks will be placed before the administration of spinal anesthesia, per our ISOC. Again, these blocks will involve the same L2-L4 and L4-S3 nerves/plexi as those for the ISOC MMPNA Block Group.

All study team members will be blinded to the nerve block treatment group/drug the patient receives/received for the described blocks. The only unblinded person regarding the study treatment will be the anesthesia team member who prepares the nerve block injection syringes, based on the randomization envelope assignment. This person who prepares the drug syringes will be otherwise uninvolved with the care of the study patient.

Table 1. Anatomic location of the analgesic nerve blocks used based on TKA versus THA

Basic description of regional anesthesia and analgesia care plan	TKA block details	THA details
Spinal anesthesia, L2-L4 and L4-S3 perineural/plexus single-injection nerve blocks	L2-L4 nerve block entails the femoral nerve in the groin. The L4-S3 nerve block entails the sciatic nerve as it emerges from the sciatic notch deep to the gluteal musculature.	L2-L4 plexus block entails the lumbar plexus within the psoas compartment, 2-3 inches lateral to the lumbar spine midline. The L4-S3 plexus block entails the lumbosacral trunk and parasacral plexus, which lies lateral to the lateral margin of the proximal sacrum. The plexus lies deep to the sacroiliac ligament.

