5.6 Sample Size Determination

Although the SF-MPQ data is the basis of our specific aim, we do not have our own preliminary SF-MPQ data. So we will base our sample size on our most robust data, that being nerve block duration from our observational data (40 hr mean, with 14 hr standard deviation). Hip replacement and knee replacement surgery are different procedures requiring anatomically different nerve blocks as described above, so we will consider these samples as separate. We consider a doubling of the nerve block duration (15 hr for plain bupivacaine, 30 hr for bupivacaine-CBD) as a clinically significant difference with respect to the military objectives of evacuation and transport. We forecast that as a single-drug (and based on historical literature), the standard deviation of plain bupivacaine duration would be half of the 15 hr projected duration (i.e., 7.5 hr). Due to likely variability in study participant responsiveness to the 4-drug mixture, we predict that the standard deviation of the bupivacaine-CBD treatment would also be half of the projected 30 hr duration (i.e., 15 hr). We believe that the 30 (SD=15) hr duration for bupivacaine-CBD is a reasonably conservative duration based on our preliminary data of 40 (14) hr block duration. Using a 2-tailed t-test with $\alpha=0.05$, 20 patients per procedure for bupivacaine treatment, and 80 patients per bupivacaine-CBD treatment would yield 95% statistical power. This sample size will also accommodate for our multiple secondary aims. Attrition of 6 active control treatment patients ($n=14$) and of 24 MMPNA-treated patients ($n=56$) will still yield just over 80% statistical power. All calculations were performed using IBM SPSS SamplePower version 3.0.1, Chicago, IL.

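### Section 5.1 does not specify arm-specific variances or a robust SE for its mixed model, although allocation is 4:1 and the plan's only variance inputs differ twofold between arms

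*Combined protocol and SAP*

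**What the plan says.** Allocation is 4:1. Section 4.1 describes the "Active Control Block Group (n=20 TKA and 20 THA patients") against 80 TKA and 80 THA patients in the 4-drug group.

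Section 5.6 sizes the trial on block duration because, for the primary instrument, "we do not have our own preliminary SF-MPQ data". It continues: "So we will base our sample size on our most robust data, that being nerve block duration from our observational data". The assumed means are "15 hr for plain bupivacaine, 30 hr for bupivacaine-CBD". The SDs differ by arm: "the standard deviation of plain bupivacaine duration would be half of the 15 hr projected duration (i.e., 7.5 hr") and, for the 4-drug arm, the "standard deviation of the bupivacaine-CBD treatment would also be half of the projected 30 hr duration (i.e., 15 hr"). The reason given for the larger value is varying patient response to the mixture. Power is computed "Using a 2-tailed t-test with $\alpha=0.05" (two-sided), for each procedure separately.

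Section 5.1 sends every hypothesis to a longitudinal multilevel model. The primary hypothesis "comparing plain local anesthetics versus ISOC MMPNA will be tested using a mixed model", with effects for treatment, surgical site and their interaction. The section states no residual or random-effect covariance structure, no variance by arm, no robust standard error and no degrees-of-freedom method. It does say that variability and normality will be looked at, and that transformed or rank-based analyses may be used where needed. Unequal variance between arms is not mentioned.

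**The concern.** A mixed model fitted with ordinary defaults estimates one residual variance for both arms. With equal arms, unequal SDs would do little harm to the arm contrast. At 4:1 they do. The pooled variance comes about 80% from the 4-drug arm, while the true uncertainty of the contrast depends heavily on the small control arm. If the larger arm is the more variable one, the standard error is too large and the test is conservative. If the smaller arm is the more variable one, the standard error is too small and the test rejects too often.

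The p-value of the primary pain contrast rests on that standard error, as would any interval reported with it. The interim looks in section 5.4 (5/20 and 10/40 per procedure) have the same 4:1 ratio and so the same exposure.

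**Working it through.** **Inputs.** From section 5.6: control mean 15 hr, SD 7.5; 4-drug mean 30 hr, SD 15; two-sided alpha 0.05. From section 4.1: n = 20 and 80 per procedure, 40 and 160 overall. SD of SF-MPQ-2: not given for either arm.

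**The plan's own figure.** Section 5.6 states 95% power at 20 vs 80.
- Pooled variance = (19×56.25 + 79×225)/98 = 192.28, so SD = 13.87.
- √(1/20 + 1/80) = 0.25, so SE = 13.87 × 0.25 = 3.467.
- Noncentrality = 15/3.467 = 4.33 on 98 df, which gives 99.0% power.

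A common SD of 15 gives 97.7%, and a Welch test gives above 99.9%. So the stated 95% does not reproduce with a standard choice of SD. It understates power, which is harmless here.

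**Pooled against true standard error, duration SDs, 20 vs 80.**
- Pooled SE = 3.467, as above.
- True SE = √(56.25/20 + 225/80) = √(2.8125 + 2.8125) = √5.625 = 2.372.
- Ratio = 3.467/2.372 = 1.46.
- Coverage ≈ 2Φ(1.96 × 1.46) − 1 = 99.6% (simulated 99.5%).

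At 40 vs 160 the pooled SE is 2.448 and the true SE 1.677, again a ratio of 1.46.

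**Same SDs with the arms swapped, 20 vs 80.** This is an assumption, not a plan input.
- Pooled variance = (19×225 + 79×56.25)/98 = 88.97, so SE = 9.43 × 0.25 = 2.358.
- True SE = √(225/20 + 56.25/80) = √11.953 = 3.457.
- Ratio = 2.358/3.457 = 0.68.
- Coverage ≈ 2Φ(1.96 × 0.682) − 1 = 82% (simulated 82%), so type I error is about 18%.

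**Range of SD ratios, 20 vs 80.** Only the first row uses SDs that the plan states, and those are for duration.

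| Control SD / 4-drug SD | Pooled SE / true SE | Coverage of nominal 95% interval |
|---|---|---|
| 0.5 (section 5.6, duration) | 1.46 | 99.6% |
| 0.67 (assumed) | 1.27 | 98.7% |
| 0.8 (assumed) | 1.14 | 97.5% |
| 1.25 (assumed) | 0.87 | 91% |
| 1.5 (assumed) | 0.79 | 88% |
| 2.0 (assumed) | 0.68 | 82% |

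**Check by simulation.** With 40,000 normal two-arm trials per case at equal means, the pooled coverages above reproduce to within about half a point. Welch coverage stays between 94.9% and 95.1%. A small random-intercept mixed model with a common variance (40 vs 160, 200 runs per case) gave SE ratios of about 1.43 and 0.61 and coverage of 99.5% and 76%. The Monte Carlo error on the 76% is about 3 points, so this confirms direction and rough size only.

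**Does the plan's fallback help?** In simulation at 40 vs 160, a Mann-Whitney test rejected a true null 1.6% of the time with the section 5.6 SDs and 11.0% with the control SD doubled. Rank methods do not remove the problem.

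**The case against.** The strongest reply is that the plan is silent, not wrong. A mixed model can carry a separate variance for each arm, and nothing in section 5.1 rules it out. A reader might infer that the planned model forbids arm-specific variances; the text does not support that. This objection stands, and the point is one of missing specification.

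A reader might also infer that the plan predicts about 82% coverage for the primary endpoint. It does not. The twofold SD ratio is for block duration, and section 5.6 has no SF-MPQ data. The direction for pain is open too. If SD rises with mean pain, control is the more variable arm. But section 5.6's stated reason for the larger SD, varied response to the mixture, points to the 4-drug arm. So do its duration inputs: under normality, Φ((24−15)/7.5) = 88% of control blocks but only Φ((24−30)/15) = 34% of 4-drug blocks would have ended by 24 hr, which leaves the 4-drug arm the more mixed population. Moreover, if SD strictly follows the mean, the SDs are equal when the means are equal. The pooled test would then have its nominal size under the null, and only interval coverage under a real difference would suffer; section 5.1 specifies a test, not an interval.

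The 46% figure has its own limit. Block duration is not in section 5.1's outcome list, and the error there is conservative with power to spare.

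Finally, these figures come from unadjusted comparisons. The planned model adjusts for baseline and concurrent health, so the residual SD ratio that matters is unknown. A log transformation, which section 5.1's fallback would permit, could also stabilise variances that scale with the mean. But that fallback does not mention unequal variance and would be chosen after seeing the data.

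**Conclusion.** The concern holds as a gap in specification and a cheap improvement. The plan combines 4:1 allocation with inputs that show an expected change in variability, and leaves the variance structure of its main model unstated. If a common variance is fitted:

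- with the section 5.6 duration SDs, the standard error is 46% too large and coverage about 99.5%, a conservative error;
- if control is the more variable arm for 24-hour pain, coverage is about 91%, 88% or 82% at assumed SD ratios of 1.25, 1.5 or 2.0.

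The second line is conditional. The documents give neither an SD nor a direction for SF-MPQ-2, so the size and sign of the error for the primary endpoint are unknown. For the same reason the sponsor cannot count on the error being conservative, and even a 1.25-fold difference in the unfavourable direction costs about 4 points of coverage (95% to 91%). The figures assume normal data and an unadjusted two-arm contrast.

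**What to change.** Add one sentence to section 5.1. For the primary 24-hour SF-MPQ-2 contrast, and for block duration if it is tested, fit the model with a separate residual variance (or covariance matrix) for each arm and Kenward-Roger or Satterthwaite degrees of freedom. Alternatively, for the single 24-hour contrast, use ANCOVA with an HC3 or Welch-type standard error. Name one of these as the planned analysis, not as a fallback chosen after inspecting the data.

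The cost is small. If the arm SDs turn out equal, intervals are about 1-2% wider overall and up to about 3% wider within one procedure. If they are unequal in the section 5.6 pattern, there is a gain: the standard error for duration at 20 vs 80 falls from 3.47 to 2.37 hr. Sample size and data collection do not change.
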